1.3 Known and Potential Risks and Benefits

OPC-61815 has never been administered to patients with heart failure. No deaths or other serious adverse events (SAEs) were reported in the phase 1 trials in healthy adult male subjects (263-08-001, 263-09-001, and 263-10-005). Feeling abnormal, feeling hot, pruritus, erythema, hyperhidrosis, nausea, epigastric discomfort, and dyspnea were the significant AEs reported following bolus intravenous administration (over 1 or 5 minutes) of OPC-61815 in Trial 263-09-001 or 263-10-005. Significant AEs were defined as those similar to feeling abnormal, pruritus, and erythema, etc. that were reported frequently in the repeated intravenous dose trial (263-09-001).

As noted earlier, OPC-61815 has not previously been administered to patients with heart failure. Nevertheless, OPC-61815 should have similar benefits to tolvaptan because, when the phosphate ester of OPC-61815 is hydrolyzed by alkali and acid phosphatase in the body, tolvaptan forms and acts as an aquaretic agent. Tolvaptan has been shown to relieve weight increase and other signs commonly observed in patients with cardiac edema (jugular venous distension, hepatomegaly, and lower limb edema).

In a clinical trial in patients with cardiac edema, the following AEs were frequently reported among 437 patients given tolvaptan (in \geq 2% incidence among tolvaptan-treated patients and at a higher frequency than in placebo-treated patients): ventricular tachycardia, constipation, dry mouth, diarrhoea, vomiting, thirst, blood urea increased, blood uric acid increased, blood creatinine increased, blood potassium increased, blood sodium increased, blood glucose increased, blood urine present, platelet count decreased, dehydration, hyperkalaemia, dizziness, pollakiuria, renal impairment, and epistaxis.

Please refer to the IB for more detailed information.

2 Trial Rationale and Objectives

2.1 Trial Rationale

Tolvaptan is approved for oral administration at 15 mg once daily in the treatment of "volume overload in heart failure when adequate response is not obtained with other diuretics (eg, loop diuretics)."

OPC-61815 is a compound based on tolvaptan of which the lower water solubility has been improved by phosphorylation of the hydroxide of the benzazepine ring. In the body, OPC-61815 is considered to be metabolized to tolvaptan via hydrolysis of the phosphate ester by alkaline and acid phosphatase, and the formed tolvaptan acts as an aquaretic agent. OPC-61815 provides an aquaretic intravenous treatment option for "congestive"

Confidential - Proprietary Information

24

heart failure patients with excessive fluid retention despite treatment with other diuretics" and should prove useful. We started clinical development of OPC-61815 in heart failure patients with persistent fluid retention despite treatment with conventional diuretics for the intended indication of "volume overload in heart failure when adequate response is not obtained with other diuretics (eg, loop diuretics)." The aquaretic effect of OPC-61815 is thought to be produced by the active metabolite tolvaptan. Because tolvaptan is widely used in heart failure patients who have fluid retention despite treatment with conventional diuretics, treating patients with placebo in a clinical trial of OPC-61815 is considered unethical. A phase 3 trial of OPC-61815 will therefore investigate the noninferiority of OPC-61815 to tolvaptan 15-mg tablet instead of using placebo as control.

Data in healthy adults show intravenous OPC-61815 at doses of 3 to 30 mg (about half the dose levels of tolvaptan tablets) achieves equivalent exposure of tolvaptan and daily urine volume to those achieved with oral tolvaptan tablets at doses of 5 to 60 mg. However, because OPC-61815 has not previously been administered to heart failure patients, the dose-exposure relationships of intravenous OPC-61815 and oral tolvaptan in heart failure patients are not yet clear. This phase 2 pharmacology trial has been planned to determine the dose of OPC-61815 injection equivalent to tolvaptan 15-mg tablet, which is used in clinical setting in heart failure patients with fluid retention despite treatment with conventional diuretics.

Based on the above, we consider the conduct of this trial is scientifically and ethically justified.

2.2 Justification for DNA storage

This trial will store deoxyribonucleic acid (DNA) samples on a voluntary basis. Sampling for DNA storage will take place only at the trial sites that have agreed to perform sampling for DNA storage prior to the trial. DNA samples will be collected only from subjects who have given consent to DNA storage in writing. In the questions and answers section of the "Clinical trials based on pharmacogenomics" (Notification No. 0930007 of the Evaluation and Licensing Division, Pharmaceutical and Food Safety Bureau issued on 30 Sep 2008), the Ministry of Health, Labour and Welfare states that collection of DNA samples from trial subjects and retention of the samples for genomic/genetic analysis related to evaluation of IMPs used in a trial (pharmacokinetics, efficacy, safety, etc.) are acceptable provided (1) the target and schedule of analysis are established at the conduct of the trial or (2) genomic/genetic analysis is planned although neither its target nor schedule has been established at the conduct of the trial.

We therefore think storing DNA samples for future analysis of the relationships between interindividual differences in the efficacy, safety, or pharmacokinetics of OPC-61815 and variations of DNA characteristics (eg, genetic polymorphism) is justified.

2.3 Dosing Rationale

(1) Dose

Tolvaptan exposure and daily urine volume reported in the single intravenous dose trial of OPC-61815 (263-08-001⁴) and single oral dose trials of tolvaptan (156-95-302⁵ and 156-00-001⁶) in healthy adults are summarized respectively in Table 2.3-1 and Table 2.3-2.

At the dose ranges tested (OPC-61815 injection 3, 7.5, 15, and 30 mg and tolvaptan tablets 5, 15, 30, and 60 mg), OPC-61815 injection at about half the dose of tolvaptan tablets achieved tolvaptan exposure and daily urine volume equivalent to those achieved with tolvaptan tablets.

Table 2.3-1 Pharmacokinetic Parameters (Mean ± Standard Deviation) of Plasma Tolvaptan Concentration in Healthy Adults After Administration of Intravenous OPC-61815 and Oral Tolvaptan							
Intravenous OPC-61815 ^a				Oral Tolvaptan			
Dose (mg)	C _{max} (ng/mL)	AUC _t (ng·h/mL)	t _{max} b (h)	Dose (mg)	C _{max} (ng/mL)	AUC _t (ng·h/mL)	t _{max} b (h)
$\begin{array}{c} 3 \\ (N=6) \end{array}$	34.58± 5.420	155.0 ± 29.76	1.0	5^{c} $(N = 6)$	48.3 ± 16.0	203.43± 80.47	1.5 ^e
7.5 (N = 6)	116.7 ± 30.23	527.5 ± 134.2	0.5	15^{d} $(N = 6)$	135.27 ± 52.58	645.4 ± 367.0	2.0
15 (N = 6)	268.8 ± 52.66	1598 ± 586.6	1.0	30 ^d (N = 12)	213.37 ± 75.75	1301.5 ± 552.6	2.0
30 (N = 6)	442.5 ± 64.87	1980 ± 535.8	0.5	60^{d} $(N = 6)$	315.22 ± 104.89	2321.4 ± 633.5	3.0

^aTrial 263-08-001, ^bMedian, ^cTrial 156-95-302, ^dTrial 156-00-001, ^eMedian calculated from individual values (only the mean is provided in the clinical study report of Trial 156-95-302)

Confidential - Proprietary Information

Version 1.0, 08 May 2017 Amdt. 1: 19 Jun 2017

Table 2.3-2 Daily Urine Volume (Mean ± Standard Deviation) of Health Adults After Administration of Intravenous OPC-61815 and Oral Tolvaptan				
]	Intravenous OPC-61815 ^a		Oral Tolvaptan	
Dose (mg)	Daily Urine Volume (mL/24h)	Dose (mg)	Daily Urine Volume (mL/24h)	
Placebo (N = 16)	2687.8 ± 1519.7	Placebo ^c $(N = 14)$	2584.5 ± 1298.4	
3 (N = 6)	3752.3 ± 465.2	5 ^b (N = 6)	2710.8± 363.3 ^d	
7.5 (N = 5)	4240.0 ± 756.2	15 ^c (N =6)	3018.5 ± 729.9	
15 (N = 6)	5810.2 ± 1213.4	30^{c} $(N = 12)$	5722.9 ± 643.2	
30 (N = 6)	7173.7 ± 1582.4	60 ^c (N = 6)	8751.5 ± 1280.6	

^aTrial 263-08-001, ^bTrial 156-95-302, ^cTrial 156-00-001, ^dDaily urine volume was calculated from individual values (only the measurements of individual collection periods are provided in the clinical study report of Trial 156-95-302)

In Japan, the approved dose and regimen of Samsca tablets, of which active ingredient is tolvaptan, is "The usual adult dosage of Tolvaptan is 15 mg once a day orally." The recommended initial dose is 7.5 mg for patients with a serum sodium concentration of less than 125 mEq/L and patients in whom a rapid decrease in plasma volume should be avoided. Because intravenous administration of OPC-61815 at about half the dose of tolvaptan tablets achieved tolvaptan exposure equivalent to tolvaptan tablets in healthy adults, this trial will administer OPC-61815 injection at 4 mg, 8 mg (respectively about half the tolvaptan tablets 7.5 mg and 15 mg), and 16 mg (double dose of 8 mg), as the doses expected to achieve effects equivalent to tolvaptan tablets.

Liver metabolism of tolvaptan is expected to be decreased in heart failure patients due to blood flow in organs and especially in the liver, compared with healthy adults. Also, the first-pass metabolism (in the gastrointestinal tract and liver) of tolvaptan tablets may differ in healthy adults and heart failure patients. Because of these matters, in heart failure patients, OPC-61815 injection at a dose about half that of tolvaptan tablets may not reproduce equivalent tolvaptan exposure to tolvaptan tablets as indicated in healthy adults.

Considering that OPC-61815 injection has not previously been administered to heart failure patients and also that OPC-61815 injection at a lower dose than indicated in

healthy adults may achieve equivalent tolvaptan exposure to that with tolvaptan 15-mg tablet, we decided to administer OPC-61815 injection at 2 mg in addition to at 4 mg, 8 mg, and 16 mg.

(2) Regimen

The once-daily administration of OPC-61815 is selected for this trial because a sufficient plasma tolvaptan exposure and daily urine volume had been achieved with the same regimen in phase 1 trials in healthy adults (263-08-001, 263-09-001, and 263-10-005⁷). In the repeated dose trial administering OPC-61815 injection intravenously for 1 minute (263-09-001), the following AEs not reported in the single dose trial that administered the injection for 5 minutes (263-08-001) were reported: feeling abnormal in 9 of 27 subjects, pruritus in 5 of 27 subjects, pruritus generalised in 3 of 27 subjects, and erythema in 3 of 27 subjects. The trial investigating the rate of intravenous injection of OPC-61815 (263-10-005) administered the drug over 2 hours, 5 minutes, and 1 minute to explore the cause of the above AEs and also to investigate the relationships between the events and the rate of administration. None of these potentially drug-related adverse events occurred when OPC-61815 injection 7.5 mg and 15 mg were administered over 2 hours.

The results of the trial indicate the risk of the above potentially drug-related adverse events may be reduced by administering OPC-61815 with longer administration duration.

The daily urine volume (mean \pm standard deviation) in the trial investigating the rate of administration is summarized in Table 2.3-3.

Daily urine volume was generally consistent regardless of the rate of administration. This suggests the diuretic effect 24 hours after administration is not likely to be affected by the rate of administration.

Table 2.3-3	Daily Urine Volume (Mean ± Standard Deviation) of Healthy Adults Following Intravenous Administration of OPC-61815 at a Dose of 7.5 mg and 15 mg Over 1 Minute, 5 Minutes, and 2 Hours			
Dose (mg)	Duration of Administration Daily Urine Volume (mL/24			
	1 minute $(N = 6)$	2576.7 ± 1412.2		
Placebo	5 minutes $(N = 6)$	2418.4 ± 764.0		
	2 hours $(N = 6)$	2272.3 ± 951.5		
	1 minute $(N = 5)$	3276.8 ± 614.1		
7.5	5 minutes $(N = 6)$	3647.5 ± 828.9		
	2 hours $(N = 6)$	3353.0 ± 861.8		
15	1 minute $(N = 6)$	5584.8 ± 953.0		
	5 minutes $(N = 6)$	4818.3 ± 1358.6		
	2 hours $(N = 6)$	4765.2 ± 1583.9		

Figure 2.3-1 illustrates the time course of urine excretion rate by the rate of administration in the trial on the rate of intravenous administration. Table 2.3-4 summarizes the t_{max} of plasma tolvaptan by the rate of administration. The initial peak of urine excretion rate was observed between 0.75 and 1.25 hours with bolus injection (administered for 1 or 5 minutes). With 2-hour administration, it was 2.75 hours. The t_{max} of tolvaptan was 0.5 to 1 hour with bolus injection and 2.3 hours with 2-hour administration. The peak urine excretion rate was observed slightly after the t_{max} , but the above results indicate shortening the t_{max} should achieve an earlier onset of action.

[figure not shown]

Figure 2.3-1 Time Course of Urine Excretion Rate After Intravenous Administration of OPC-61815 at a Dose of 7.5 mg and 15 mg Over 1 Minute, 5 Minutes, and 2 Hours

of OPC-61815	t _{max} of Tolvaptan Following Intravenous Administration of OPC-61815 at a Dose of 7.5 mg and 15 mg Over 1 Minute, 5 Minutes, and 2 Hours		
	t _{max} (h) of Plasma Tolvaptan		
Duration of administration Dose	1 minute	5 minutes	2 hours
7.5 mg	0.50	1.00	2.30
15 mg	0.75	0.50	2.30

(Median)

PK models of plasma OPC-61815 and tolvaptan concentration were created using data from the prior phase 1 studies (263-08-001, 263-09-001, and 263-10-005) for simulation of change in pharmacokinetic parameters of OPC-61815 and tolvaptan by the rate of administration. The simulated pharmacokinetic parameters of tolvaptan following administration of OPC-61815 injection 8 mg are summarized in Table 2.3-5. The simulation showed no significant differences in the AUC_{24h} or C_{max} of tolvaptan across the duration of administration. This suggests similar effects regardless of the duration of administration. However, the observed differences in t_{max} indicate the duration of administration may affect the time to onset of action. The t_{max} of tolvaptan was 1, 1.5, and 2.25 hours after bolus (1 or 5 minutes), 1-hour, and 2-hour intravenous injection of OPC-61815, respectively. The difference in t_{max} between bolus injections, which was over 1 hour by 2-hour intravenous injection, was estimated to decrease to about 30 minutes by 1-hour intravenous injection. The t_{max} of tolvaptan after administration of tolvaptan 15-mg tablet is 2 hours. Therefore, these results suggest that, if OPC-61815 is administered intravenously over 1 hour, compared with tolvaptan tablets, an earlier t_{max} of tolvaptan and an earlier onset of action should be achieved.

Table 2.3-5	Simulated Pharmacokinetic Parameters of Tolvaptan Following Intravenous Administration of OPC-61815 at a Dose of 8 mg for 1 Minute, 5 Minutes, 1 Hour, and 2 Hours				
Duration of administration	AUC 24h (h·ng/mL) (mean ± standard deviation)	C _{max} (ng/mL) (mean ± standard deviation)	t _{max (h)} (median)		
1 minute	521.5 ± 141.2	115.1 ± 24.12	1		
5 minutes	531.5 ± 145.5	115.5 ± 23.86	1		
1 hour	521.1 ± 142.6	109.6 ± 22.07	1.5		
2 hours	522.5 ± 144.4	99.93 ± 20.11	2.25		

Early onset of action (eg, for relief of dyspnea) is desired in some patients hospitalized with heart failure. This trial will intravenously administer OPC-61815 at 2 mg, 4 mg, 8 mg, and 16 mg over 1 hour in CHF patients to investigate the dose and regimen of OPC-61815 equivalent to once-daily tolvaptan 15-mg tablet.

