- Subjects with a history of hypersensitivity or idiosyncratic reaction to benzazepine or benzazepine derivatives such as mozavaptan hydrochloride and benazepril hydrochloride
- Subjects who are severely obese (body mass index [BMI], body weight [kg]/height [m]² exceeding 35 kg/m²)
- Subjects with supine systolic blood pressure of <90 mmHg
- Subjects with any of the following laboratory test abnormalities: Total bilirubin, >3.0 mg/dL; serum creatinine, >3.0 mg/dL; serum sodium >147 mEq/L; serum potassium, >5.5 mEq/L
- Subjects with concurrent symptoms or history of hepatic impairment
- Subjects who are unable to sense thirst or who have difficulty with fluid intake

Trial Site(s): Approximately 40 trial sites in Japan

Investigational
Medicinal Product(s),
Dose, Dosage
regimen, Treatment
period, Formulation,
Mode of
Administration:

Lyophilized formulation containing 2, 4, 8, or 16 mg of OPC-61815 or placebo in a vial and tolvaptan 15-mg tablet or placebo tablet.

This trial will be conducted using a double-dummy design to maintain blindness. Subjects will receive a combination of either OPC-61815 injection and placebo tablet or placebo injection and tolvaptan 15-mg tablet. Once daily for 5 days either tolvaptan 15-mg tablet or placebo tablet will be orally administered, followed immediately by 1-hour intravenous administration of either OPC-61815 at 2, 4, 8, or 16 mg or placebo.

As there will be a difference in appearance between the OPC-61815 solution and the placebo solution at the time of preparation, the person responsible for IMP preparation at the trial site (non-blinded staff) will prepare the double-blinded IMP, which will then be administered by the investigator or subinvestigators, etc.

Trial Assessments:

Pharmacokinetics: Blood sampling for measurement of plasma concentrations of parent drugs and metabolites

Pharmacodynamics: Blood sampling for serum concentrations of sodium and potassium, serum osmolality, and biomarker measurements; and urine sampling or cumulative urine volume collection for daily urine volume, daily fluid balance, daily urine sodium excretion, daily urine potassium excretion, urine osmolality, and daily fluid intake

Efficacy: Body weight, congestive symptoms (lower limb edema, other edema, jugular venous distension, pulmonary congestion confirmed by chest X-ray, pulmonary rales, third cardiac sound, and hepatomegaly), cardiothoracic ratio, and NYHA classification

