Tolvaptan is an arginine vasopressin V₂ receptor antagonist synthesized by Otsuka Pharmaceutical Co., Ltd. (Hereinafter Otsuka Pharmaceutical). It specifically inhibits the binding of arginine vasopressin (AVP) to the V₂ receptor in the distal nephron to increase water excretion without affecting electrolyte excretion (aquaretic effect). For typical symptoms of congestive heart failure (CHF) include dyspnea, orthopnea, and jugular venous distension, 1 diuretics are widely used in the treatment of these symptoms. 2,3 Conventional diuretics (mainly loop diuretics) exert their diuretic effect by increasing electrolyte excretion in the urine. This mechanism of action makes them difficult to be a therapeutic option for patients with decreased serum electrolyte levels. Because conventional diuretics can also impair renal function at high dose levels, dose increase is not always an option even when adequate response is not obtained. In contrast, a greater diuretic effect can be expected with tolvaptan because of its different mechanism of action compared with other conventional diuretics. Moreover, tolvaptan does not lower serum electrolyte levels and has little effect on renal function, making it an option for patients who are not suitable for dose increase or prolonged treatment with conventional diuretics.

In Japan, tolvaptan was approved in 2010 under the trade name of Samsca® tablets for the indication of "volume overload in heart failure when adequate response is not obtained with other diuretics (eg, loop diuretics)." In 2013, a new indication of "body fluid retention in hepatic cirrhosis when adequate response is not obtained with other diuretics (eg, loop diuretics)" was approved. In 2014, another indication of "control of the progression of autosomal dominant polycystic kidney disease with increased renal volume and rapid renal volume growth" was granted for the drug. Outside Japan, in 2009, tolvaptan was approved in the United States for "treatment of hyponatremia with normal fluid volume or clinically significant volume overload in patients with heart failure or syndrome of inappropriate antidiuretic hormone secretion (SIADH)" and in Europe for "hyponatremia secondary to SIADH." In 2015, an additional indication of "control of the progression of rapidly progressive autosomal dominant polycystic kidney disease with stage 1 to 3 chronic renal failure" was granted in Europe. Tolvaptan has been approved in over 40 countries/regions.

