3.2 Trial Treatments

3.2.1 Dose and Regimen and Duration of Treatment

The dose levels and formulations for each group are summarized in Table 3.2-1. The investigator or subinvestigator will administer either one tolvaptan 15-mg tablet or placebo tablet once a day with water, immediately followed by intravenous administration of either OPC-61815 injection at 2 mg, 4 mg, 8 mg, or 16 mg or placebo for 1 hour (acceptable range: 55 to 65 minutes) according to a separate written procedure for IMP administration. Each dose should be administered promptly after the patient completes urine sampling (for daily urine volume measurement) after breakfast each day during the 5-day treatment period. The time of administration (start time of administration) on Day 2 and later should be not more than 20 minutes before or after the time of administration (start time of administration) on Day 1. After confirming each

Confidential - Proprietary Information

34

dose has been administered, the investigator or subinvestigator documents the start and finish time of administration (for injection) or the date and time of administration (for tablet) in source documents and case report form (CRF). The IMP is to be administered even if the patient fails to eat breakfast that day.

Table 3.2-1 Dose Levels and Formulations per Group				
Group	OPC-61815 Dose	Formulation(s) (per day)		
Tolvaptan 15-mg tablet	0 mg/day	1 vial of placebo injection, 1 tolvaptan 15-mg tablet		
OPC-61815 injection 2 mg	2 mg/day	1 vial of OPC-61815 injection 2 mg, 1 placebo tablet		
OPC-61815 injection 4 mg	4 mg/day	1 vial of OPC-61815 injection 4 mg, 1 placebo tablet		
OPC-61815 injection 8 mg	8 mg/day	1 vial of OPC-61815 injection 8 mg, 1 placebo tablet		
OPC-61815 injection 16 mg	16 mg/day	1 vial of OPC-61815 injection 16 mg, 1 placebo tablet		

[Rationale for duration of treatment]

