3.4.4 Exclusion Criteria

Subjects will be excluded if they meet any of the exclusion criteria in Table 3.4.4-1.

A subject excluded as a result of falling under any of the exclusion criteria may be rescreened if any changes in the condition resulting in falling under the exclusion criteria are observed. For rescreening, the subject will be asked to follow the procedure described in Section 3.9.

Confidential - Proprietary Information

Tabl	e 3.4.4-1 Exclusion Criteria
1	Subjects with acute heart failure
2	Subjects with mainly noncardiogenic congestive symptoms
3	Subjects who are on an ventricular assist device
4	Subjects who have the following diseases, complication, or conditions:
	Subjects who are suspected of having hypovolemia
	Hypertrophic cardiomyopathy (excluding dilated phase)
	Valvular disease with significant valvular stenosis; or
	Hepatic encephalopathy with difficulty in adequate fluid intake
5	Subjects who have experienced acute myocardial infarction within 30 days prior to the screening examination
6	Subjects with definite diagnosis of active myocarditis or amyloid cardiomyopathy
7	Subjects who have the following diseases, complication, or conditions: • Poorly controlled diabetes mellitus
	• Anuria
	Dysuria associated with urinary tract obstruction, calculus, or tumor
8	Subjects who have the following history of disease:
	History of sustained ventricular tachycardia or ventricular fibrillation within 30 days prior to the screening examination among subjects without an implantable cardioverter defibrillator
	History of cerebrovascular disease (excluding asymptomatic cerebral infarction) within 6 months prior to the screening examination
	Subjects with a history of hypersensitivity to any of ingredients of OPC-61815 or tolvaptan
	History of hypersensitivity or idiosyncratic reaction to benzazepines or benzazepine derivatives such as mozavaptan hydrochloride and benazepril hydrochloride
9	Subjects who are severely obese (body mass index [BMI], body weight [kg]/height [m] ² exceeding
	35 kg/m^2)
10	Subjects with supine systolic blood pressure of <90 mmHg
11	Subjects with any of the following laboratory test abnormalities:
	Total bilirubin, >3.0 mg/dL; serum creatinine, >3.0 mg/dL; serum sodium >147 mEq/L; serum
	potassium, >5.5 mEq/L
12	Subjects with concurrent symptoms or history of hepatic impairment (including subjects with
	aspartate aminotransferase (AST) or alanine aminotransferase (ALT) at the screening examination

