8.1 Packaging and Labeling

Trial medication will be provided to the IMP manager by the sponsor or designated agent. IMPs will be provided as subject kits. Each kit consists of 8 vials of OPC-61815 injection (2 mg, 4 mg, 8 mg, 16 mg, or placebo) and a small box containing a blister sheet of 10

tolvaptan tablets (15-mg tablet or placebo). A label stating that the content is for clinical trial use, protocol number, IMP names, quantity, lot number, expiration date, storage conditions, and sponsor's name and address will be affixed to each vial and small box. Each subject kit also displays the statement that the content is for clinical trial use, protocol number, drug number, IMP names, quantity, lot number, expiration date, storage conditions, subject identifier, and sponsor's name and address.

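### Entry criteria set no lower serum sodium limit, so a patient below 125 mEq/L could start above the 7.5-mg dose that section 2.3 reports as recommended (precautionary gap, low severity)

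*Protocol*

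**What the plan says.** - **Reported starting dose.** Protocol 2.3 gives 15 mg once daily as the usual approved tolvaptan dose in Japan and adds: "The recommended initial dose is 7.5 mg for patients with a serum sodium concentration of less than 125 mEq/L". The same recommendation covers patients in whom plasma volume should not fall quickly.
- **Eligibility.** Criterion 11 in Table 3.4.4-1 excludes "serum sodium >147 mEq/L", and the Synopsis repeats it as "serum sodium >147 mEq/L; serum potassium, >5.5 mEq/L". No inclusion, run-in or other exclusion criterion sets a lower sodium limit. The rationale given for criteria 11 to 13 is safety, without detail.
- **Dosing.** Table 3.2-1 fixes the daily dose by arm. The control arm, for example, receives "1 vial of placebo injection, 1 tolvaptan 15-mg tablet". Under section 8.1 the kits hold only 15-mg or placebo tablets. Allocation is 1:1:1:1:1 (section 3.6.1), and no reduced start or titration is described.
- **Uncertainty in this population.** Section 1.3 states that "OPC-61815 has never been administered to patients with heart failure". Section 2.3 warns that an injection at about half the tablet dose "may not reproduce equivalent tolvaptan exposure to tolvaptan tablets as indicated in healthy adults".
- **Safeguards.** Subjects are inpatients. Sodium is measured at screening; on Day 1 before dosing, at 4 to 6 h and at 8 to 12 h; and before each later dose. During the treatment period the site measures it as well as the central laboratory. Section 3.8.3.1 stops treatment for a rise of 12 mEq/L or more within 24 h or a level of 155 mEq/L or more. Criterion 17 lets the investigator exclude anyone judged unsuitable.

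**The concern.** The protocol cites a sodium level below which a lower tolvaptan start is recommended. It then neither applies that level at entry nor says why full dosing is acceptable below it. With fixed doses and a blinded investigator, nobody can give such a patient the lower start or steer them to a low-dose arm.

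The safeguards with numeric limits act after dosing. The infusion ends within 55 to 65 minutes, and the first postdose sodium is drawn at 4 to 6 h. Stopping treatment can therefore withhold Day 2, but not the Day 1 dose, and it is the initial dose that the recommendation addresses. At stake is a safety precaution in the compound's first use in heart failure. The primary pharmacokinetic comparison is largely unaffected.

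**Working it through.** The plan states no figure on this point. The nearest is its rule that the injection matches a tablet of about twice the dose: 4 mg to 7.5 mg and 8 mg to 15 mg, with 16 mg twice the 8-mg dose. On that rule the 15-mg tablet, injection 8 mg and injection 16 mg lie above the reported start. That is 3 of 5 arms, or 60% under equal allocation.

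**Exposure reference for a 7.5-mg tablet.** No 7.5-mg oral data are given, so two estimates are made from Table 2.3-1 (5 mg: AUCt 203.43, Cmax 48.3; 15 mg: AUCt 645.4, Cmax 135.27).
- Log-log interpolation, value at 5 mg × 1.5^b with b = ln(value at 15 mg / value at 5 mg) / ln 3. AUC: b = 1.051, giving 311.5. Cmax: b = 0.937, giving 70.6.
- Half the 15-mg values: AUC 322.7, Cmax 67.6.

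**Ratios.** Each arm's AUC and Cmax are divided by both references. Injection inputs are the simulated 1-hour infusion of 8 mg (Table 2.3-5: AUC24h 521.1, Cmax 109.6) and the observed injections of 7.5 mg (AUCt 527.5, Cmax 116.7) and 30 mg (1980, 442.5) in Table 2.3-1, scaled in proportion to dose.

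| Arm | Source | AUC; Cmax | Ratio to 7.5 mg oral |
|---|---|---|---|
| Tablet 15 mg | observed | 645.4; 135.27 | 1.92–2.07 |
| Injection 16 mg | simulated 8 mg × 2 | 1042.2; 219.2 | 3.10–3.35 |
| | 30 mg × 16/30 | 1056; 236 | 3.27–3.49 |
| | 7.5 mg × 16/7.5 | 1125.3; 249.0 | 3.49–3.68 |
| Injection 8 mg | simulated | 521.1; 109.6 | 1.55–1.67 |
| | 7.5 mg × 8/7.5 | 562.7; 124.5 | 1.74–1.84 |
| Injection 4 mg | simulated 8 mg / 2 | 260.6; 54.8 | 0.78–0.84 |
| | 7.5 mg × 4/7.5 | 281.3; 62.2 | 0.87–0.92 |
| Injection 2 mg | simulated 8 mg / 4 | 130.3; 27.4 | 0.39–0.42 |
| | 7.5 mg × 2/7.5 | 140.7; 31.1 | 0.44–0.46 |

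The observed 15-mg injection is left out because its AUCt is out of line: 1598/527.5 = 3.03 from 7.5 to 15 mg, but 1980/1598 = 1.24 from 15 to 30 mg. Leaving it out lowers the 16-mg estimate: 1598 × 16/15 = 1704.5, which would be 5.3 to 5.5 times on AUC.

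**The 4-mg arm in heart failure.** It would pass the reference if exposure from the injection relative to the tablet were higher than in healthy adults by a factor of 1/0.92 = 1.09 to 1/0.78 = 1.28. Section 2.3 allows for a shift in this direction, since it says a lower injection dose may match the 15-mg tablet.

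**Number affected.** The share of patients below 125 mEq/L is not in the documents. Assumed shares of 0%, 1% and 5% of 55 dosed patients give 0, 0.55 and 2.75 patients; times 3/5, these give 0, 0.33 and 1.65 in the three higher arms.

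**The case against.** The strongest reply is that section 2.3 reports a label recommendation for oral tolvaptan. It is not a contraindication or a trial rule, and it advises a lower start rather than no treatment. The label does not cover OPC-61815, so carrying it to the injection arms relies on a healthy-adult relation that the protocol itself doubts. Low-sodium patients may also belong in the target population: the Introduction calls conventional diuretics a difficult option when serum electrolytes are reduced, and says tolvaptan does not lower them. Sodium is watched closely, criterion 17 permits exclusion, and section 3.7.1.4 requires an eligibility check before dosing. Amendment 1 followed regulator questions on the exclusion criteria.

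Most of this stands, and it keeps the severity low. A reader might infer that criterion 11 contradicts section 2.3, or that the trial breaches the label. The documents support neither, because a reported recommendation does not bind eligibility. What remains is that criterion 17 and the predose check carry no sodium threshold. Amendment 1 lists only a hypersensitivity criterion as the change to the exclusions, so it does not show that low sodium was considered.

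The recommendation's second group, patients who should avoid a rapid fall in plasma volume, has no numeric cut-off. It is partly covered by the exclusion of suspected hypovolemia, so no further criterion is proposed for it.

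**Conclusion.** The point holds as a precautionary safety gap of low severity that is cheap to close. A patient below 125 mEq/L would have a 3 in 5 chance of an arm above the reported start, at the multiples in the table. The count of three rests on healthy-adult data, and the 4-mg arm could join them.

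The multiples are approximate. The reference is interpolated or halved from groups of six, and the 5-mg data come from a separate trial in Caucasian men. The observed injections lasted 5 minutes, AUCt is set against AUC24h, and dose proportionality is assumed.

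A reader might take 3.1 to 3.7 times the exposure as evidence of a sodium hazard in the 16-mg arm. The documents do not support that: these are exposure ratios, not risks of overly rapid sodium correction, and the number of patients concerned may be zero.

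**What to change.** 1. In Table 3.4.4-1 criterion 11 and in the Synopsis, write: *serum sodium <125 mEq/L or >147 mEq/L*.
2. In section 3.7.1.4 (3), add: *Before the first dose, the sodium limits in criterion 11 are checked against the site-measured Day 1 predose value; a subject outside either limit is not dosed.*

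No new test is needed: screening sodium, the Day 1 predose site sodium and the eligibility check before administration are already planned. The site must have its result in hand before dosing. The SAP needs no change, because every analysis set requires at least one dose and SAP 7.1 counts randomised and dosed subjects separately. The targets of 11 starters and 10 sampled subjects per group also stand.

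The costs are a slightly smaller eligible pool, no data below 125 mEq/L before phase 3, and an occasional subject who is randomised but not dosed. Under section 3.9 that subject cannot be rescreened, because rescreening is limited to those not yet allocated. If the sponsor prefers to keep these patients, a sentence of rationale in section 2.3 would record the decision but would not add the predose check.
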